15.5 Study Records Retention

Study records will be maintained for at least three years from the date that the grant federal financial report (FFR) is submitted to the National Institutes of Health (NIH) or longer as dictated by local IRB or state laws/regulations.

As outlined by IRB regulations, data will be destroyed in an appropriate and safe way (e.g., files will be securely deleted from computers).

The file connecting patients' names with their unique identification number will be kept in a password-protected file by the CC and on the GPI's computer for a minimum of three years, in accordance with IRB regulations, before being securely erased.

15.6 Protocol Deviations

A protocol deviation (PD) is any noncompliance with the clinical study protocol or GCP principles. The noncompliance may be on the part of the patient, practitioner, SPI, or study staff. As a result of deviations, corrective actions are to be developed by the study staff and implemented promptly. All deviations from the protocol must be addressed in study subject source documents and promptly reported to NIDCR and the local IRB, according to their requirements.

Any PD that is reportable to an IRB must also be reported to NIDCR. NIDCR defers to the IRB for reporting time-frame requirements. Once a PD has been reported to an IRB, action must be taken to report the deviation to NIDCR. If the IRB overseeing the study protocol requires annual reporting of PDs to their IRB, that reporting frequency is acceptable to NIDCR. At the time of each Medical Monitor report, all previously unreported PDs must be reported in the Medical Monitor report independent of when they are reported to IRBs.

16 PUBLICATION/DATA SHARING POLICY

This study will comply with the [NIH Public Access Policy](#), which ensures that the public has access to the published results of NIH funded research. It requires scientists to submit final peer-reviewed journal manuscripts that arise from NIH funds to the digital archive [PubMed Central](#) upon acceptance for publication. All study personnel are required to read in its entirety and agree to abide by the network's "Data Analysis, Publications, and Presentations Policies" document. The current version of this policy is always kept at the network's public web site at <http://nationaldentalpbrn.org/publication.php>.

Appendix A: Schedule of Events

Appendix B: Examples of Anterior Openbite

Appendix C: Method to Measure Millimetric Vertical Relapse from Photographs

Appendix D: Patient Retention Plan

APPENDIX A: Schedule of Events

Procedures	Practitioner Screening/ Enrollment	¹ Patient Enrollment/ Baseline (Stage 1 [S1])	^{1,2} Appliance Removal, End of Active AOB Treatment (Stage 2 [S2], Visit 1 [V1]; ~24 months after S1)	Retainer Check Visits (S2, V2-X)	³ Final Study Visit (Stage 3; S2, V1 +10 to 24 months)
Practitioner Recruitment and Enrollment	X				
Obtain Practitioner Characteristics	X				
Informed Consent		X			
Assessment of Eligibility Criteria		X			
Review of Medical/Dental History		X			
Obtain/confirm contact information and preferred method of contact		X	X	X	X
Patient Demographics		X			
Enrollment Visit data collection (Patient and Practitioner)		X			
Cephalometric x-ray		X	X		
Intra-oral frontal photograph		X	X		X
Measurement of the height of right maxillary central incisor			X		X
End of Active Treatment data collection (Patient and Practitioner)			X		
Retainer Use data collection (Patient and Practitioner)				X	
Final Visit data collection (Patient and Practitioner)					X

Foot notes:

1 = Cephalometric x-rays and intra-oral frontal photographs obtained as part of routine orthodontic care before treatment and at the time of appliance removal/end of active AOB treatment will be used.

2 = One additional intra-oral frontal photograph will be obtained at the time of appliance removal/end of active AOB treatment for this research.

3 = Two intra-oral frontal photographs will be obtained approximately one year after end of active treatment for this research.

APPENDIX B: Examples of Anterior Openbite

Figure 1. Severe Anterior Openbite

Figure 2. Dental Openbite

Figure 3. Skeletal Openbite

Figure 4. Initial

Figure 5. Post-Treatment

Figure 8. Initial

Figure 9. End of orthodontic treatment

Figure 10. 1 year post-treatment

Appendix C: Method to measure millimetric vertical relapse from photographs

1. Two intra-oral frontal photos will be taken at the end of treatment, as well as at the one-year follow-up time, to measure overbite. One photo will be taken in maximum intercuspation (Fig A), while the other will be taken with the incisors apart so that the entire length of the mandibular incisor can be visualized (Fig B).
2. The practitioner will also measure and report the clinical height of right maxillary incisor at the end of active treatment and at the one-year follow-up, to the nearest tenth of a mm. This measurement will be used to calculate the magnification factor.
3. At each time point, both photos are cropped to exactly capture the width of the four maxillary incisors, with an image size of 6 inches in length to facilitate measurement. Then, the height of the maxillary right central is measured, and the length of the visible portion of the mandibular right central incisor is measured in both photos.

Figure A: Maximum intercuspation

Figure B: Incisors apart

4. If the photos above were viewed with a length dimension of 6 inches, then the maxillary right incisor height would be measured at 61 mm, and the lower incisor would be measured at 36 mm in Fig A and 43 mm in Fig B. We can then calculate the overbite by this method:

61 mm divided by 15.3 (clinically measured height of incisor) = 3.99 mm. This is the magnification factor.

43 mm - 36 mm = 7 mm. This is the overbite prior to adjusting for magnification.
7 mm divided by 3.99 = 1.8 mm of overbite

5. The same method will be employed to calculate the overbite at the end of the one-year retention period, and then the change in overbite can be calculated by subtracting the end of treatment overbite from the one-year follow-up overbite. For example, if the patient's overbite is measured at 1.1 mm using one-year follow-up photos, then the amount of change is 2.4 - 1.1 = 1.3 mm.

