11.3 Final Analysis Plan

Analysis plan for Primary Objectives:

Primary objective #1 is to estimate the proportion of patients who are successfully treated. As described in section 3.2 (outcome measures), successful treatment is defined as occurring when patients have positive overlap at the end of treatment; this will be calculated with a 95% confidence interval.

Though not an explicit hypothesis, we expect those that are “successfully” closed will have had a smaller distance between the maxillary and mandibular incisor tips prior to treatment, i.e., at enrollment, than those not successfully closed. We will calculate the mean distance improved separately for those successfully treated and those not. It may be that those not successfully treated had more improvement than those who were successfully treated (if the former had a greater distance that needed to be corrected) and we want to capture this. Thus, as an additional but secondary measure of improvement, we will also calculate mean and median distance improved as descriptive measures.

Primary objective #2 is to estimate, among patients who are successfully treated, the proportion of patients whose treatment is stable. As described in section 3.2 (outcome measures), stability will be assessed one year after end of active treatment. The primary measure (strictest, most conservative classification) will be among patients who are determined to have been successfully treated at end of active treatment (having closed their AOB), what proportion of these have positive overlap at the one-year follow up time. This proportion will be estimated with a 95% confidence interval. Additional assessments of stability will include the proportion of all who had improvement in overbite (positive increases) during retention, no change in overbite during retention, and worsening of overbite (negative increases) during retention. We will calculate these mean and median changes as descriptive measures.

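### The Appendix C photographic overbite cannot fall below zero, so millimetric relapse into open bite is truncated, and the worked example of change is wrong in value and sign

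*Protocol*

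**What the plan says.** Section 3.2 measures stability in two ways: a yes/no judgement of incisal overlap, and a millimetric overbite from photographs, because no cephalogram is taken at one year. On the cephalograms the same section treats overbite as a signed quantity, negative when there is no overlap.

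Appendix C sets out the photographic method. One photograph is taken in maximum intercuspation (Fig A) and one with the incisors apart, so that the whole lower incisor shows (Fig B). Step 3 states that "the length of the visible portion of the mandibular right central incisor is measured in both photos". In step 4, "the lower incisor would be measured at 36 mm in Fig A and 43 mm in Fig B". The magnification comes from "61 mm divided by 15.3 (clinically measured height of incisor) = 3.99 mm", and the result is "7 mm divided by 3.99 = 1.8 mm of overbite". No step measures a vertical gap.

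Step 5 defines change by "subtracting the end of treatment overbite from the one-year follow-up overbite". Its example supposes 1.1 mm at one year and ends "then the amount of change is 2.4 - 1.1 = 1.3 mm".

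Section 11.3 uses this change in its additional assessments of stability. These are the proportions improved, unchanged and worse, with positive change as improvement and "worsening of overbite (negative increases) during retention" as the third class, plus mean and median change as descriptive measures.

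**The concern.** The study is about open bite, yet its millimetric measure of relapse cannot record one. It registers loss of overlap down to edge-to-edge and then stops. A patient whose bite reopens slightly and one whose bite reopens widely receive the same value, and a patient who stays open receives about the same value at both visits whatever happens in between.

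The photographs are the only millimetric source at one year, so no second measurement can correct this. The rule is written out in full in the protocol, and an analysis plan cannot restore a gap that the image readers were never asked to measure.

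The example adds a second problem. Readers and programmers tend to copy worked examples, and this one gives a relapse a positive sign, which Section 11.3 counts as improvement.

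**Working it through.** **Inputs** (Appendix C, steps 4 and 5): upper incisor height 61 mm on the image and 15.3 mm clinically; lower incisor visible length 36 mm (Fig A) and 43 mm (Fig B); one-year overbite 1.1 mm.

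**Step 4 reproduces.** Magnification = 61 / 15.3 = 3.987. Overbite = (43 - 36) / 3.987 = 1.756, which rounds to 1.8 mm. The magnification is a ratio, although the text labels it mm.

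**Step 5 does not reproduce.**
- By the stated rule, change = 1.1 - 1.8 = -0.7 mm (-0.66 unrounded).
- The example prints 2.4 - 1.1 = +1.3 mm. The 2.4 appears nowhere else in Appendix C. To obtain it from step 4 would need a clinical height of 61 × 2.4 / 7 = 20.9 mm instead of 15.3, or an image difference of 2.4 × 3.987 = 9.6 mm instead of 7.
- Even with 2.4 mm, the stated direction gives 1.1 - 2.4 = -1.3 mm.

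**Floor at zero.** Let L be the full lower incisor length, on the clinical scale. Fig B shows L. Fig A shows L - max(true overbite, 0). The Appendix C value is therefore L - [L - max(true overbite, 0)] = max(true overbite, 0). Applying this to pairs of illustrative true values at the right central incisor (mm):

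| End of treatment | One year | True change | Appendix C change |
|---|---|---|---|
| 1.8 | 1.1 | -0.7 | -0.7 |
| 1.8 | -0.5 | -2.3 | -1.8 |
| 1.8 | -2 | -3.8 | -1.8 |
| 1.8 | -4 | -5.8 | -1.8 |
| -1 | -3 | -2 | 0 |
| -3 | -1 | +2 | 0 |
| -1 | +0.5 | +1.5 | +0.5 |

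The method is exact while there is overlap at both visits. Otherwise the recorded change is pulled towards zero. A closed patient who reopens is still classed as worse, but by too little. A patient open at both visits loses the direction of change as well.

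**Size in the cohort.** The protocol gives no overbite distribution, so only an assumed range can be shown. Suppose that all patients in the summary are closed at the right central at end of treatment, and that one-year overbite there is normal with mean 0. The floor then shifts the mean change upwards by 0.40 × SD: 0.40 mm for an SD of 1.0 mm, and 0.80 mm for an SD of 2.0 mm. With a higher one-year mean the shift is smaller.

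For patients not closed at end of treatment, the planning rates in Section 11.2 give at most 840 × 0.90 × 0.30 = about 227. At one year this is about 181 (840 × 0.90 × 0.30 × 0.80) or 202 (840 × 0.80 × 0.30), depending on whether the 20% attrition is additional or total. How many of these are open at the right central is unknown.

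**The case against.** The strongest reply is that nothing confirmatory uses the affected quantity. Primary stability is the yes/no overlap judgement, made separately from Appendix C. Objectives 3a and 3b (Section 11.4.2) use stability as a binary variable. The millimetric improvement in objective 2a comes from signed cephalograms. The sample size rests on proportions. Section 11.3 itself calls the mean and median changes descriptive. All of this stands, and it limits the severity.

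The reply also disposes of several stronger readings:
- **The primary stability proportion is biased.** It is not, for the reason just given.
- **Half of the closed patients sit at the floor, because planning assumes 50% stability.** This does not follow. Section 5.1 defines open bite by lack of overlap at any incisor, while Appendix C reads only the right central. A patient may fail at another incisor and stay above the floor.
- **Every patient never closed is scored as unchanged.** This applies only to those open at the right central at both visits. One who gains overlap is scored as improved, by too little. It also depends on reading the word all in Section 11.3 as including patients not closed at end of treatment, which is unclear. Measurement error will in any case rarely give an exact zero.
- **Relapse will be analysed as improvement.** The stated rule in step 5 has the right direction and agrees with Section 11.3. Only the illustration is reversed, and it could be read as a magnitude.

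Finally, measurement is central, with quality procedures left to a manual that is not shown (Section 13), and practitioners record open-bite status at follow-up (Section 7.1). Neither cures the gap. The status form is not described as a millimetric measure, and the protocol's own measuring rule should not depend on a manual to reverse it.

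**Conclusion.** Wrong as written, of moderate severity. Followed literally, Appendix C returns the larger of true overbite and zero, so it truncates relapse in the patients whose bite reopens at the right central incisor. The affected results are the mean and median change during retention and, through patients open at both visits, the improved, unchanged and worse proportions. The bias is towards stability. Individual errors can be large: 4.0 mm of a 5.8 mm relapse is lost in the widest case tabulated. The average effect cannot be fixed from the protocol, because it depends on the spread of overbite at one year and on how many patients are open at the right central.

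The truncation of relapse among closed patients holds however the word all in Section 11.3 is read. The errors in the step 5 example need no assumption: on the protocol's own figures and rule the answer is -0.7 mm, not +1.3 mm.

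**What to change.** Add to Appendix C, step 3: when the incisal edges do not overlap in the intercuspation photograph, measure the vertical gap between the upper and lower right central incisal edges, divide it by the same magnification factor, and record it as negative overbite. Apply this at both end of treatment and one year.

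Correct the step 5 example to 1.1 - 1.8 = -0.7 mm and state that a negative change means relapse, as in Section 11.3.

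In Section 11.3, say whether the improved, unchanged and worse proportions cover all patients with both measurements or only those closed at end of treatment.

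The cost is wording and a little reader time. The photographs and the clinical incisor height are already collected, so no visit or procedure is added, and images already read can be measured again.

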- 3) Make contact with participating offices every three months to review progress of patients in treatment, upcoming appliance removal dates, and upcoming one-year post treatment dates. Offices will then contact patients, as needed, to remind them of key upcoming dates. The patient's preferred method of contact (e.g., postal mail, email, telephone, text message) will be ascertained at the baseline appointment. Experience has shown that it is personal relationships, both between the patients and offices, and the offices and the RCs, that promote successful execution of PBRN studies. In other words, it will be more meaningful for patients to hear from their personal dental offices regarding a reminder for a study appointment. In turn, it will be more meaningful for the office to hear from its RC that it is time for them to contact patients. Experience has also shown that it is beneficial for the network to relieve burden on the practices. To that end, the National Dental PBRN will request IRB approval for the RCs and for the CC to receive the patient contact information and the contact information of two persons, one of whom that does not live in the same household as the patient, so that both can assist the practices with follow-up contacts (e.g., birthday cards, appliance removal visit reminders, etc), particularly with patients who have had difficulty attending visits. The regions will have some latitude in determining the best means for maintaining contact with study patients and ensuring their ongoing participation.
- 4) Number of Patients per Practitioner Considerations:
 - a. Ask practitioners to enroll approximately 3 - 8 patients, but no more than 15 patients per practitioner, preferably in an approximately 11 months enrollment period. Recruiting in a limited time period will make it easier to recall and follow the patients.
- 5) Given the above design features, patients should not be "lost". However, if a patient moves and contact is lost, the CC has extensive experience with using tracing resources such as National Change of Address services, motor vehicle departments, and LexisNexis databases. In those cases, the CC will implement those tracking procedures.
- 6) The process for contacting patients for appliance removal and subsequent follow-up visit and reminders will be for the practice to make the initial contact attempts, then inform their RC if there was no response within three weeks of the second contact attempt. In this situation, the RC will discuss the circumstances with the practice staff, and a decision will be made on allowing the office to attempt additional contacts, or if the RC should attempt to contact the patient. (For example, a phone number that is discontinued would prompt the RC to attempt to contact the patient, whereas a patient who has a history of periodic out-of-town travel for work might not.) If the office feels the RC should get involved, the RC will attempt to contact the patient. If the RC is unable to contact the patient after

2 attempts, then the RC should inform the CC, and the CC will initiate tracking procedures to identify updated patient contact information. If the office feels the RC should not get involved, then the RC will check again with the office every 2 weeks to see if the office has been successful in contacting the patient, or if the RC needs to get involved. Initiating tracking procedures promptly when there is no patient response to contact attempts will minimize missed study visits and also minimize loss to follow-up.

Methods to Minimize “Missing Data”

- 1) Because patients will be in various stages of participation, it will be important to fully train office personnel about all stages of the study, as well as the data that must be collected at each stage. Having said that, enrollment will be emphasized during the first 6 months, followed by the active treatment stage, and finally, the retention stage. RCs will periodically remind offices about the active treatment and retention data collection procedures, as well as to assist them with tracking the progress of each patient through the course of the study. It can be challenging to remember to perform study procedures when the enrollment phase is over and data collection is only occurring in the office every few months.
- 2) Ask participating offices to develop a system to flag records of patients in their practices who are participating as patients in the study, as well as to flag study patients in the office schedule. In this way, study personnel will be alerted to the fact that the patient is at the office, and can ensure that data collection takes place if indicated. Flagging the patient in the schedule will help to ensure that patients are not inadvertently scheduled when the practitioner will not be in the office. In the same way, if a patient’s record is requested by another office, study personnel can inform the RC and attempts made to maintain the patient in the study.
- 3) Emphasize to practitioners as part of their initial study packages that the dentist has to be the motivational director of the study, especially regarding follow-up appointments, and make sure that the staff understands that the office is committed to participating in the study and seeing it through to completion.

Methods to Minimize “Refused”

- 1) The method described in the 1st point above under “Lost” will also help reduce the number of patients who refuse to continue participating. At enrollment, patients are informed that they are agreeing/consenting to participate in a long-term follow-up study. Patients who enroll are required to state a willingness to participate throughout the study.
- 2) The method described in the 3rd point above under “Lost” (making contact between visits) should also help reduce refusals. The CC has found that

retention is increased if patients are kept engaged and interested in the study through the use of periodic newsletters and other study updates, postcards, birthday cards, phone calls, using the patient's preferred mode of contact. Additionally, follow-up involvement will be kept as simple and convenient for the patient as possible.

Methods to Minimize “Unable”

- 1) There are several scenarios in which a patient stops seeing the original/enrolling practitioner:
 - a. Patient does not move, but:
 - i. Patient changes practitioner - in same practice
 - ii. Patient changes practitioner - in different practice
 - iii. Patient stops seeing any practitioner
 - b. Patient moves
 - i. Patient sees new practitioner
 - ii. Patient stops seeing any practitioner
 - c. Practitioner retires or dies
 - d. Practitioner moves
 - e. Practitioner refuses to continue participating (low likelihood)
- 2) The operational impact of all of the above scenarios can be summarized by two scenarios:
 - a. Patient has a new practitioner (not a National Dental PBRN member)
 - b. Patient stops seeing any practitioner
- 3) Locating the patient should not be a problem (see Methods to Minimize “Lost”), and having the patient agree to continue participating should not be a problem (see Methods to Minimize “Refused”).
- 4) The main operational issue is: How to get study follow-up visit information from patients seeing a non-National Dental PBRN practitioner or not seeing any practitioner. If allowable by the IRB, we propose the following options:
 - a. Invite the new dentist into the Network so the patient can continue to be followed by the new practitioner.
 - b. Ask the patient to return to the original practitioner only to collect the end of treatment and one year post-treatment data.
 - c. Ask the patient to visit a different network practitioner who is participating in the study only to collect study related data.
 - d. If the patient is moving, provide a list of network practitioners in the area the patient is moving to.

Other Administrative and Design Methods to Increase Retention Rates

- 1) IRB/Informed Consent Considerations to Reduce Attrition

- a. Incorporate into the informed consent form (ICF) permission for all relevant study personnel, both in the dentist's office as well as the study investigators, and RCs to contact the patient. This will allow communications with the patient by study personnel without having to go through the dental office.
 - b. Incorporate into the ICF permission to see a National Dental PBRN practitioner other than the initial provider for the purpose of data collection. This will expedite data collection in those instances where a National Dental PBRN practitioner retires or sells his/her practice, or where a patient goes to a different non-National Dental PBRN practitioner, or stops seeing a practitioner for routine care.
- 2) Financial, but non-coercive incentive to patients to encourage continuing participation.
- a. Patients will receive \$25 each for the enrollment and end-of treatment visits. For the final study visit, which is approximately after one year of retainer use, they will receive \$50. This amount is purposely larger than the other two, as it is always more difficult to retain patients after active treatment has been completed.

Additional methods for patients who have missed an appliance removal or subsequent follow-up Visit

- 1) If an enrolled patient misses the appliance removal or subsequent follow-up window for a visit, his or her contact information will be confirmed through the CC tracking procedures prior to the practice initiating contact attempts for the recall visit scheduling and the recall reminder for the next recall visit.
- 2) The practitioner's office will use the confirmed contact information to attempt to contact the patient by telephone (or other preferred means of contact) to schedule the next recall visit in a timely fashion, or remind the patient of the recall visit.
- 3) If successful in contacting the patient, there will be special emphasis on reminding the patient of the importance of his/her participation in the study and the importance of complying with the study visits.
- 4) If the patient cannot be reached, the two individuals designated as additional connections to the patient will be contacted to confirm the patient's contact information and/or determine the patient's whereabouts and additional attempts will be made to make contact with the patient.
- 5) If their designees cannot be contacted, CC tracing resources will be used in an attempt to locate the patient to schedule the visit, or remind them of the visit.
